9.2.2 Neuroimaging Review

Local review of MR imaging studies at each site and central review of the MR imaging studies will be conducted through the PBTC Neuroimaging Center (NIC). NIC review will include assessment of response to therapy (as feasible). The director and one neuroradiologist of NIC will review the imaging studies at study completion. If the local and central review are not in agreement the NIC neuroradiologist will confer with the participating site to determine why there is a discrepancy via conference call.

10 STUDY CALENDAR

Data is to be submitted according to the Data submission timelines located on the PBTC-051 webpage.

	Pre-therapy	Course 1-2	Courses 3- Course 36	Completion/ Off Treatment
Physical Assessments				
Medical history	X	Weekly	X ^A	X
Physical exam /height/weight	X	Weekly	X ^A	X
Vital signs	X	Weekly	X ^A	X
Pulse oximetry	X	Weekly	X ^A	X
Performance status	X	Weekly	X ^A	X
Neurologic exam	X	Weekly	X ^A	X
Laboratory Evaluations				
CBC ^B (WBC, HgB, Platelets, ANC, ALC)	X	Weekly	X ^A	X
Serum Chemistry ^B (Sodium, Potassium, Bicarbonate, Chloride, Calcium, BUN, Creatinine, Glucose, Phosphorous, Magnesium, Albumin, Total Protein)	X	Weekly	X ^A	X
SGPT(ALT), SGOT(AST), Total Bilirubin ^B	X	Weekly	X ^A	X
Serum or Urine pregnancy test ^C (for females of childbearing potential)	X	X ^A	X ^A	
CD4 cell count ^J	X			
B cell count (CD19 cells in blood)	X	X ^H	X ^H	X
Serum Immunoglobulin G (IgG)	X	X ^A	X ^A	X
Coagulation (PT, INR, aPTT) ^D	X			
ECG (QTc)	X			
Echocardiogram or MUGA scan	X			X
CSF Cytology (if clinically indicated) ^G	X ^G	X ^G		
Imaging Assessments				
Brain MRI (standard) ^E	X	X	X	X
Spine MRI (if clinically indicated) ^I	X ^I	X ^I	X ^I	X ^I
Correlative Studies^F				
Pharmacokinetic Studies ^F	X	X	X	
Anti-Drug Antibody Assay ^F	X	X	X	X
Circulating Cytokines ^F	X	X	X	
T cell phenotyping ^F	X	X	X	

Tumor Mutational Burden Assessment ^F (PBMC and tumor tissue) (Whole Exome Sequencing)	X			

A. To be completed prior to each course.
 
B. To be done more frequently throughout the duration of treatment if required to monitor toxicities.
 
C. Within 72 hours prior to starting treatment, if eligibility pregnancy test is within 72 hours, no need to repeat prior to Course 1.
 
D. Coagulation tests include PT, INR, and aPTT; INR is only required at screening and as clinically indicated thereafter.
 
E. Patients will have MRI Brain with and without contrast performed within 3 weeks prior to enrollment, at the end of course 2, every 3 courses through course 14, and then every 4 courses till the end of therapy, and at the time of disease progression or completion of treatment.
 
F. All the correlative studies are required. See section 9.1 for collection schedule and sample requirements.
 
G. Cerebrospinal fluid assessment via lumbar puncture or Ommaya tap for patients with clinical concern for disseminated disease per the discretion of the treating physician.
 
H. B cell count will be tested pre-therapy, at the end of course 2, every 3 courses through course 14, and then every 4 courses till the end of therapy, and at the time of disease progression or completion of treatment.
 
I. Spine MRI should be performed prior to therapy and at the same time points as standard Brain MRI, if clinically indicated.
 
J. CD4 cell count should be tested pre-therapy for patients with history of autologous bone marrow/stem cell transplant.
				

11 MEASUREMENT OF EFFECT

Although the clinical benefit of APX005M has not yet been established, the intent of offering this treatment is to provide a possible therapeutic benefit, and thus the patient will be carefully monitored for tumor response and symptom relief in addition to safety and tolerability. Patients with measurable disease will be assessed by standard criteria. For the purposes of this study, patients should have MRI scan within 3 weeks prior to enrollment, at the end of course 2, every 3 courses through course 14, and then every 4 courses till the end of therapy, and at the time of disease progression or completion of treatment. In addition to a baseline scan, confirmatory scans will also be obtained 9 weeks following initial documentation of an objective response.

11.1 Therapeutic Effects

11.1.1 Definitions

- Evaluable for Toxicity

Patients who receive at least 1 dose of APX005M and are removed from treatment for toxicity during the dose-finding period (first 6 weeks of treatment) are evaluable for estimating the MTD.

Patients who have completed all therapy during the dose-finding period but who failed to comply with all the specified clinical and laboratory monitoring requirements during the DLT observation period may be considered inevaluable for estimating the MTD and replaced.

Patients who receive less than two doses of the protocol specified therapy and who go off treatment for reasons other than toxicity (e.g., progressive disease, withdrawal of consent, etc.) during the dose finding period will be considered inevaluable for estimating the MTD and will be replaced.

- Evaluable for Objective Response

Only those patients who have measurable disease present at baseline, have received at least one dose of therapy, and have had their disease re-evaluated will be considered evaluable for response. These patients will have their response classified according to the definitions stated below. (Note: Patients who exhibit objective disease progression prior to the first scheduled MRI will also be considered evaluable.)

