5.1 Agent Administration

5.1.1 APX005M (CD40 agonistic mAb)

APX005M dosing will begin at 0.1 mg/kg, which is one dose level below the adult recommended phase 2 dose. For APX005M, both 1 mg/kg and 0.6 mg/kg were explored in adult participants, and the adverse events at 0.6 mg/kg were manageable and reversible. The APX005M dose will be increased in subsequent cohorts until the MTD is reached or until dose level 3 is complete without MTD being defined (

Table 2). No inpatient dose escalation will be permitted on the protocol. Only DLTs observed during the dose-finding period (the first 2 courses, i.e., the first 6 weeks of treatment) will be used to guide dose escalation. Dose escalation will be governed by the statistical design as described in section 13 of the protocol.

Table 2

Dose Escalation Schedule		
Dose Level	Dose of APX005M (mg/kg, IV, Q3 weeks)	round final dose to
0	0.03 mg/kg	2 decimals
1* (starting dose level)	0.1 mg/kg	1 decimal
2	0.3 mg/kg	1 decimal
2.5	0.45 mg/kg	1 decimal
3	0.6 mg/kg	1 decimal
Note: Dose level 2.5 will only be studied if dose level 3 is deemed to be too toxic.		

Subjects will be assigned a dose level at the time of enrollment. APX005M will be administered at the assigned dose level on Day 1 of each course 21 day. Patients may continue to receive APX005M for 36 courses (approximately 2 years) or until disease progression, unacceptable toxicity or death, whichever occurs first. Delays between courses for reasons other than toxicity may occasionally occur however dosing should follow the treatment plan as closely as possible.

Dosing should be adjusted based on weight (kg) calculated at the beginning of each course of therapy. The dose may be prescribed using the weight that was determined at the prior visit. However, if the current weight is $\geq 5\%$ different from the prior weight, the prescription should be revised.

Accrual to Stratum 1 was completed as of May 14, 2020. Dose level 3 (0.6mg/kg) was determined to be the recommended phase 2 dose for Stratum 1. The starting dose for Stratum 2 (the DIPG cohort) was set to be one dose level below the RP2D determined in the non-DIPG patients (Stratum 1) (also see Section 13.1.3). Therefore, accrual to Stratum 2 was initiated at dose level 2 (0.3mg/kg). Accrual to Stratum 2 remains open at the time of this amendment.

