5.2.1 Dose-Limiting Toxicities (DLT's)

- Any APX005M-related adverse event during the first 2 courses of therapy (6 weeks, 42 days) that leads to a dose reduction or results in the permanent cessation of therapy will be considered dose limiting. All dose modifications in all courses are to follow the guidelines provided in Section 6.2.
- Any APX005M-related adverse event during the first 2 courses of therapy that results in a delay of treatment > 2 weeks.

5.2.1.1 Non-hematologic dose limiting toxicity is defined as:

- Any grade 4 non-hematologic toxicity
- Any grade 3 non-hematologic toxicity with the exception of:
 - Grade 3 nausea and vomiting < 5 days
 - Grade 3 diarrhea responding to optimal medical treatment within 5 days
 - Grade 3 elevation of transaminases that returns to levels meeting eligibility criteria within 7 days of study drug interruption and does not recur upon restarting drug.
 - Grade 3 fever or infection of fewer than 5 days in duration

- Grade 3 hypophosphatemia, hypokalemia, hypocalcemia or hypomagnesemia that are asymptomatic and responsive to oral supplementation
- Grade ≥ 3 cytokine release syndrome
- Toxicity related to treatment with APX005M which delays scheduled re-treatment for > 2 weeks, or >1 week for cytokine release related complications.

5.2.1.2 Hematologic dose limiting toxicity is defined as:

- Any grade 4 hematologic toxicity with the exception of lymphopenia
- Grade 3 neutropenia with fever
- Grade 3 thrombocytopenia on 2 separate days or requiring a platelet transfusion on 2 separate days within a 7 day period.

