5.2.3 Dose Escalation/ De-escalation

Dose escalations/de-escalation decisions will be based on the 3+3 design as described in the statistical section of the protocol. The initial cohort of three (3) patients will be treated at 0.1 mg/kg (the dose levels to be tested are listed in

Table 2). Only DLTs observed during the dose-finding period of therapy will be used to guide dose escalation/de-escalation.

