6.2 Hematologic and Non-hematologic Adverse Events and Management

6.2.1 Dose Modifications for Hematologic Toxicity

Dose adjustments are based on nadir blood counts since the preceding administration of investigational product.

If a patient experiences dose-limiting hematological toxicity as outlined in Section 5.2.1.2, APX005M treatment will be reduced to the next lower dose level. If the toxicity resolves to meet on study parameters within 14 days of drug administration, provided there is no current active bleeding in the case of dose-limiting thrombocytopenia, the patient may resume therapy at one dose level lower. Patients who are dose-reduced for toxicity will not have their dose re-escalated. If toxicity does not resolve to meet on study parameters within 14 days of drug administration, the patient must be removed from protocol therapy. Two dose-reductions per patient are allowed. If any dose-limiting toxicity occurs in a patient already dose-reduced twice for toxicity, the patient must be removed from protocol therapy. APX005M dose adjustments for hematologic toxicity during treatment are described in Table 3.

Table 3: APX005M Dose Modifications for Hematologic Toxicity

APX005M related toxicity	APX005M dose modification
Grade 4 Neutrophil count decrease	Dose reduction
Grade 3 Neutrophil count decrease with fever	Dose reduction
Grade 4 Thrombocytopenia	Dose reduction
Grade 3 Thrombocytopenia on 2 separate days or requiring a platelet transfusion on 2 separate days within a 7 day period	Dose reduction

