13 STATISTICAL CONSIDERATIONS

13.1 Study Design/Endpoints

13.1.1 Stratification Factors

Stratum 1: Recurrent or Refractory Patients

Patients with a histologically confirmed diagnosis of a primary malignant CNS tumor that is recurrent, progressive, or refractory.

Stratum 2: Newly diagnosed DIPG - previously this stratum was on hold until the pediatric RP2D was established in Stratum 1 patients. Stratum 1 was closed to accrual on May 14, 2020 and dose level 3 (0.6 mg/kg APX005M) was declared to be the RP2D in Stratum 1. This stratum is now open to accrual.

Patients with diffuse intrinsic pontine gliomas (DIPGs) will be eligible 6 to 14 weeks post-completion of radiation therapy if without evidence of progression.

13.1.2 Dose Finding for Stratum 1

This is a safety and dose finding study of APX005M in pediatric patients with malignant brain tumors. The starting dose level for this study will be dose level 1 (0.1 mg/kg) with possible escalation to 2 additional dose levels barring safety concerns. The DLT observation period will be the first 2 cycles (42 days). Given the relatively limited safety data available with this agent and none in pediatrics, we have chosen to use the 3+3 design for dose escalation due to its conservative nature with respect to cohort sizes. For the 3+3 designs, dose escalations are planned in cohorts of three patients. No intra-patient escalation will be allowed and dose escalation will not be considered until toxicity information is available from at least 3 evaluable patients at the current dose level. Based on this approach, the MTD will be empirically defined as the highest dose level at which six patients have been treated with at most one patient experiencing a DLT and the next higher dose level has been determined to be too toxic. If the lowest dose level studied is too toxic or the highest dose level studied is considered safe, the estimate of the MTD will not be available. In the event that dose level 3 is deemed to be too toxic following escalation from dose level 2, dose level 2.5 will be studied as an intermediate level.

If all the dose levels are investigated with acceptable toxicity, consideration will be given to investigating higher dose levels based on discussions between the study committee and the sponsor. If a decision is made to not study higher doses and six patients have been treated safely at the highest dose level, then the highest dose level may be recommended for further study in Phase II trials.

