The recommended phase II dose (RP2D) will be based on the MTD and the totality of the safety/efficacy data. Once the MTD or a RP2D is identified, the total number of patients treated at the MTD/RP2D will be increased to 12 to further define the toxicity profile. In the event that excessive toxicities are observed in these additional patients, the MTD/RP2D may be revised and de-escalation to a lower dose level may occur.

In the event of a single fatal toxicity, the OBDMC will suspend enrollment, pending discussion with the study chair, the PBTC Toxicity Monitoring Committee, the PBTC DSMB and others as necessary.

13.1.3 Safety Study for Stratum 2

Barring excessive toxicity, we expect to enroll approximately 12 evaluable DIPG patients in Stratum 2 after pediatric RP2D has established in Stratum 1 to assess the safety of this agent in patients with non-progressive DIPG post radiation therapy. The starting dose for the DIPG cohort

will be one dose level below the RP2D determined in non-DIPG patients where 3 patients will be enrolled. If no DLTs are observed then we will escalate to the RP2D where we will treat 6 DIPG patients simultaneously. If 1 DLT is observed in 3 patients then we will enroll 3 additional patients at the starting dose level. If 2 or more DLTs are observed at the starting dose level then de-escalation to a lower dose level will be considered and a similar approach will be repeated. If no more than 1/6 patients experience a DLT at the starting dose level then we will escalate to the RP2D established in Stratum 1 and open 6 slots simultaneously to evaluate the safety of this dose in DIPG patients. In the event that we have to de-escalate to a lower dose level, we will require that 6 patients are treated with no more than 1 DLT at the dose that is determined to be the RP2D in this stratum.

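### Section 11.1.1 makes early non-toxicity leavers inevaluable for the MTD and replaces them, with no exception for a DLT already observed; one clarifying sentence is needed (minor)

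*Combined protocol and SAP*

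**What the plan says.** Section 11.1.1 (Evaluable for Toxicity) has three rules.

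1. A patient who has had at least one dose and is removed for toxicity in the dose-finding period is evaluable for the MTD.
2. A patient who completed therapy but missed required monitoring may be treated as inevaluable and replaced. This is discretionary.
3. "Patients who receive less than two doses of the protocol specified therapy and who go off treatment for reasons other than toxicity" in the dose-finding period "will be considered inevaluable for estimating the MTD and will be replaced". This is mandatory. Progression and withdrawal of consent are given as examples.

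The first and third rules turn on the recorded reason for leaving, not on whether a DLT occurred.

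A DLT does not always end treatment. Section 5.2.1 says that a related event in the first two courses "that leads to a dose reduction or results in the permanent cessation of therapy will be considered dose limiting". Section 6.2.1 says that after a dose-limiting hematologic toxicity that resolves in time, "the patient may resume therapy at one dose level lower". Table 4 in Section 6.2.2 gives dose reduction as the action for some non-hematologic events that 5.2.1.1 counts as DLTs, such as grade 3 cytokine release syndrome of up to 7 days.

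On the counts, Section 13.1.2 (Stratum 1) says that "dose escalation will not be considered until toxicity information is available from at least 3 evaluable patients at the current dose level". Section 13.1.3 (Stratum 2) states its decisions in terms of DLTs observed, but its enrolment target is in evaluable patients: "we expect to enroll approximately 12 evaluable DIPG patients in Stratum 2".

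**The concern.** A patient has a DLT after dose 1, is due to continue at a reduced dose, and then withdraws consent or progresses before dose 2. The patient has had one dose and left for a reason that is not toxicity, so the third rule applies word for word: the patient is inevaluable and replaced. Nothing in 5.2.3, 13.1.2 or 13.1.3 restores the event to the count.

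Stratum 2 decisions turn on one event. No DLT in 3 escalates, one in 3 expands to 6, and at most one in 6 escalates. If these counts use evaluable patients, dropping one DLT can change 1/3 to 0/3, or 2/6 to 1/6, provided the replacement has no DLT. Section 5.1.1 states that Stratum 2 is still accruing, so the wording is in use.

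**Working it through.** The plan gives no error rate or operating characteristic for this rule, so there is no figure to reproduce. The check has a textual part and an illustration.

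**Text**

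- *Sections 5.1.1 and 5.2.3.* The latter reads: "Only DLTs observed during the dose-finding period of therapy will be used to guide dose escalation/de-escalation". This limits by time which DLTs count. It does not make a patient evaluable, so it neither contradicts 11.1.1 nor supplies the exception.
- *Section 5.4.2.* It lists unacceptable toxicity, with a pointer to 5.2.1, as an off-treatment reason. Read alone, that could make every DLT a removal for toxicity and hence evaluable. But 6.2.1 and Table 4 allow continuation after some DLTs, and 5.4.2 lists refusal and progression as separate reasons. The gap stays open, and these sections disagree on whether a 5.2.1 event is in itself an off-treatment reason.
- *Section 13.1.3.* It supports either denominator: it acts on DLTs observed, but plans in evaluable patients. Section 2.2.2 reports dose level 3 in Stratum 1 as 2 DLTs in 12 evaluable patients.

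**Illustration**

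Inputs:
- *p*, the true DLT rate: 33.3% (assumed), and 16.7% = 2/12, the rate observed at 0.6 mg/kg in Stratum 1 (Section 2.2.2).
- Half of DLTs fall before dose 2 (assumed), so p1 = p2 = p/2.
- l1 and l0, the non-toxicity exit before dose 2 with and without a course-1 DLT. Both are assumed, because Section 2.2.2 gives no reasons for the two inevaluable patients among 14 at dose level 3.

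DLT rate in the counted set:
- Literal rule: r = [p1(1−l1) + p2(1−l0)] / [p1(1−l1) + (1−p1)(1−l0)]. If l1 = l0, r = p.
- With an exception for observed DLTs: the same formula with l1 = 0.

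Probability of escalating from the Stratum 2 starting level under 13.1.3: (1−r)³ + 3r(1−r)⁵.

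At p = 33.3%, l0 = l1 = 10%:
- Literal: r = 0.300/0.900 = 33.3%; 0.296 + 0.132 = 42.8%.
- Exception: r = 0.3167/0.9167 = 34.5%; 0.280 + 0.125 = 40.5%.

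At p = 16.7%, l0 = l1 = 10%:
- Literal: r = 0.150/0.900 = 16.7%; 0.579 + 0.201 = 78.0%.
- Exception: r = 0.1583/0.9083 = 17.4%; 0.563 + 0.201 = 76.4%.

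The first *n* patients counted with the exception always contain at least as many DLTs as the first *n* counted without it, so any disagreement has the literal count escalating. The differences, 42.8 − 40.5 = 2.3 points and 78.0 − 76.4 = 1.6 points, are therefore also the share of trials in which the two counts decide differently.

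Sensitivity of the literal rule to l1, at p = 33.3% and l0 = 10%:

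| l1 | r | P(escalate) | P(at most 1/6) |
|---|---|---|---|
| 0% | 34.5% | 40.5% | 32.8% |
| 10% | 33.3% | 42.8% | 35.1% |
| 20% | 32.1% | 45.3% | 37.6% |
| 30% | 30.8% | 47.9% | 40.4% |

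With l1 = 10% and p = 33.3%, at least one DLT is dropped among 3 enrolled with probability 1 − (1 − 0.0167)³ = 4.9%, and among 6 with probability 9.6%.

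**The case against.** The strongest reply is that Stratum 1 is closed and Stratum 2 has its own rule. Section 11.1.1 speaks of estimating the MTD. Section 13.1.3 is a safety study that does not use that term and acts on DLTs observed, so a course-1 DLT blocks the zero-DLT path whatever the patient does next. That is a fair reading, and it means the change from 1/3 to 0/3 is possible rather than prescribed. It does not settle the matter, because 13.1.3 also plans in evaluable patients and the only toxicity evaluability definition is in 11.1.1.

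The reply is also right on size. Many DLT patients are taken off for toxicity under Section 6 and stay evaluable. If half are (assumed), the 1.6% disagreement at a 16.7% DLT rate falls to about 0.8%. Stratum 2 patients enter without progression and the first scheduled on-study MRI is at the end of course 2, so the exit would mostly be withdrawal or clinical progression. The event stays in the toxicity summaries of 13.3 and in the totality of safety data behind the RP2D.

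A reader might infer that 11.1.1 contradicts 5.1.1 and 5.2.3. It does not; those sections set only a time limit. A reader might also infer that the rule favours escalation on average. The documents give no exit rate by DLT status. With equal exit the average bias is zero, and if DLT patients leave less often the literal rule is slightly conservative.

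**Conclusion.** The omission holds; severity is minor. Followed literally, a mandatory rule can discard an observed DLT, and the plan does not say which patients the Stratum 2 counts include. That conclusion rests on the text alone and needs no exit rate.

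The size rests on assumptions: 10% exit in both groups, half of DLTs before dose 2, and counting on evaluable patients. On these, the decision at the starting level differs in roughly 2 trials in 100.

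A reader might suspect that a DLT was lost in Stratum 1, or that its RP2D is unsafe for this reason. The documents do not support that. No such case is recorded, and the one DLT reported in cycle 1 was counted.

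**What to change.** Add to 11.1.1: *Any eligible patient who receives at least one dose and has a DLT in the dose-finding period is evaluable for the MTD/RP2D decision and is not replaced, whatever the later reason for leaving treatment.* The word *eligible* matters, because Section 2.2.2 sets aside a patient found ineligible after starting treatment.

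State in 13.1.3 that the counts out of 3 and out of 6 are made on this evaluable set. Sections 5.4.2 and 6.2 must also be reconciled on whether a 5.2.1 event is in itself an off-treatment reason; which way is for the study committee.

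The cost is a sentence and a cross-reference, with no extra patients. The downside is a slight conservative bias, because DLT-free early leavers are still replaced while DLT patients are kept: an apparent 34.5% for a true 33.3% at 10% exit among patients without a course-1 DLT. In return, the count no longer depends on why a patient with a DLT left or how that reason was recorded.
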